## 6. Written Informed Consent – 21 CFR 50 Protection of Human Subjects

Patients who meet general entry criteria will be asked to sign the registry-specific, Institutional Review Board (IRB) -approved Informed Consent form before any registry-specific data are collected. The informed consent will be reviewed and approved by Cardiva Medical prior to IRB submission to ensure compliance with all applicable requirements of 21 CFR 50.

Since this is a post-market registry, subjects will be treated and followed according to the institution's accepted standard of care and in adherence with the protocol.

There are no additional tests. Standard of care for office visit follow-up timing for these subjects varies between sites and procedure-types, therefore a wide window for the office visit has been established to accommodate as many subjects as possible. The required office visit may be performed between 1-15 days post-procedure, followed by a telephone follow-up between 23-37 days for final assessment of any complications. These contacts are required so that Procedure Success can be evaluated at 30 days, and to ensure that outcomes are consistently reported according to industry standards.

Study personnel should explain that even if a patient agrees to participate in the registry and signs an informed consent form, the Investigator may still determine that the patient is not a suitable candidate for the registry.

A Screening/Enrollment Log will be maintained to document select information about candidates who are consented, but who are not enrolled due to failure to meet the entry criteria.

## **7. Study Procedures and Enrollment**

### **7.1. Duration of Subject Participation**

Subjects enrolled in the registry will participate for approximately 30 (+/- 7) days.

### **7.2. Enrollment**

At the completion of the endovascular procedure, patients who meet all the pre- and intra-operative eligibility criteria may be enrolled in the registry and are eligible to receive the VASCADE VCS for access site hemostasis as part of the registry. The Investigator will acknowledge intention to enroll the patient prior to VASCADE VCS insertion into the procedural sheath, and it will be documented on a source worksheet. Once Investigator acknowledgement has been made and the device has entered the body, the subject is considered enrolled into the registry and should complete all evaluations and follow-up requirements. An Enrollment Notification eCRF must be completed and submitted within 24 hours to notify Sponsor of enrollment.

If a patient does not meet all eligibility criteria for the registry, the patient may receive one of the following to achieve arterial hemostasis, at the Investigator's discretion: 1) the VASCADE VCS as a commercial device, but the subject will not be enrolled in the registry; 2) another commercially available closure device; or 3) manual compression. These patients and the final reason for registry exclusion will be documented on the Screening/Enrollment Log.

### 7.3. Event Schedule

Table 1 outlines the required registry assessments.

**Table 1. Registry Event Schedule**

	Up to 8 Weeks Before Procedure	Procedure	Post-Procedure/ Hospital Discharge	1-15 Days Post-Procedure	23-37 Days Post-Procedure
Informed Consent 	X				
Demographics/ Medical History / Risk Factors	X				
Index limb assessment 	X		X	X	X
Femoral access site assessment (angiographic)		X	X	X	X
Anticoagulant/antiplatelet regimen 	X	X	X		
Pre-op Inclusion / Exclusion Criteria assessment	X				
Laboratory tests 	X				
Intra-procedural Exclusion Criteria assessment & acknowledgement of intent to enroll		X			
Treated with VASCADE VCS		X			
TTH determination		X			
TTA determination			X		
TTD determination			X		
Procedure Success		X			X
Adverse Events 		X	X	X	X
Office Visit				X	
Telephone follow-up					X

 If informed consent is obtained > 30 days prior to procedure, the subject's verbal re-confirmation of consent should be documented in the medical record prior to the procedure.

 Index limb assessment includes Rutherford Classification, assessment of peripheral pulses, any wounds, amputation history and/or planned amputation, existing neuropathy, and ambulatory status.

 Specific medication regimen within 24 hours prior to enrollment through completion of index procedure.

 For subjects on warfarin, INR should be taken within 24 hours before procedure. "Laboratory tests" refer to exclusion criteria requirements, according to standard of care for these procedures at each site.

 Required adverse event reports: serious, device-related injury or death; minor or major access site closure-related complications; any event that is deemed by Investigator to be clinically significant AND related to the device, the access site or the index limb (See Section 13).

## **7.4. Study Procedures**

### **7.4.1. Pre-Operative (up to 8 weeks before procedure)**

After informed consent and prior to the subject's scheduled procedure, obtain:

- Medical history and risk factors
- Surgical and interventional procedural history
- Demographics (age, race, gender, ht, wt)
- Index limb assessment (Rutherford Classification, pulses, wounds, previous amputation, existing neuropathy, ambulatory status)
- Screening laboratory draws (according to institution's standard of care):
  - Serum creatinine
  - Platelet count
  - Hemoglobin and hematocrit
  - Within 24 hours of the procedure, obtain an INR for subjects on warfarin
  - Pregnancy test, as applicable to institution's standard of care.
- Medication regimen: anticoagulant / antiplatelet agents taken within 24 hours prior to index procedure.

### **7.4.2. Intra-Operative**

For consented subjects that meet the pre-operative eligibility criteria, record the relevant data regarding their endovascular procedure.

Prior to enrollment, record the following procedural information:

- ACT, if available based on institution's standard of care, (for subjects receiving unfractionated heparin)
- anticoagulants and/or antiplatelet agents administered
- access site information, including angiographic assessment and antegrade access techniques employed
- diameter and length of the introducer sheath
- vessels treated during intervention
- contralateral access information, if applicable (e.g., prior to antegrade access but during index procedure)
- known planned staging of procedure, including minor amputation and

additional interventions prior to study exit.

At the end of the endovascular procedure, with the procedural sheath in place and under fluoroscopic visualization, an injection of contrast will be made to assess the anatomy of the access site, the integrity of the procedural sheath (i.e., no kinking) and to verify the intra-operative eligibility criteria.

**NOTE: This image must be recorded and printed for the subject's records.**

#### 7.4.3. Access Site Closure

The VASCADE Vascular Closure System should be deployed following the procedure in the Instructions for Use (IFU) provided in Attachment 2. While the procedure is being performed, record the following information on the Procedure Source Data Worksheet provided by the Sponsor (required):

- **T1:** time antegrade access achieved (i.e., time of stick)
- **T2:** time endovascular procedure is completed (i.e., last guide catheter removed and final sheath is in place)
- **T3:** time of sheath fluoro/angio to confirm that procedural sheath placement is correct and not kinked (print for subject's record)
- **T4:** time VASCADE VCS is inserted into the procedural sheath
- **T5:** time that VASCADE VCS was deployed and/or removed and adjunctive compression started\*
- **T6:** time that arterial hemostasis was achieved
- Verification that arterial hemostasis was confirmed 5 minutes later
- Determination of Device Success
- Light compression methods implemented after TTH was achieved
- VASCADE VCS device specifications.

\*Immediate formation of a hematoma post-sheath removal may indicate a back-wall or secondary arterial puncture. If this situation is suspected, the VCS should be removed and the subject should be converted to manual compression according to institution's standard guidelines.

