#### Adjunctive Compression Guidelines:

Upon successful deployment of the VASCADE VCS, adjunctive compression at the site may be used until arterial hemostasis is achieved (i.e., no pulsatile bleeding or a forming hematoma). TTH will not be recorded until adjunctive compression is no longer applied and arterial hemostasis is achieved. These times will be recorded on the Procedure Source Data Worksheet provided by the Sponsor (required).

**NOTE: Manual compression devices should not be used for achieving initial arterial hemostasis to ensure accurate recording of TTH.**

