## **8. Assessment of Procedural Outcomes**

### **8.1. Primary Procedural Outcomes - Performance**

Time to hemostasis (TTH) is defined as the elapsed time between Cardiva VASCADE™ VCS removal and first observed and confirmed arterial hemostasis. The time to hemostasis will be measured in hour (hh):minutes (mm):seconds (ss). (TTH = T6 – T5).

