## 9.2.2. Performance Outcomes

### 9.2.2.1. Primary Performance Outcome Analysis (TTH)

The primary performance outcome to be described is time to hemostasis (TTH) as defined in Section 8.1. Summary statistics for TTH (mean, standard deviation, median, minimum, and maximum) will be reported for the ITT and PP subject cohorts, and as described in Section 9.1. Ninety-five percent confidence intervals will be presented for means and medians. The proportions of enrolled Cardiva VASCADE™ VCS subjects converted to manual compression will also be reported.

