#### ADJUNCTIVE COMPRESSION

Moderate manual compression at the arteriotomy site immediately after VASCADE VCS deployment, applied as an adjunctive measure to facilitate TTH. Adjunctive compression time will be included in TTH; any light manual pressure held for tissue tract oozing should be documented separately.

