### Effectiveness Results

**Table 4** summarizes the primary efficacy endpoint, Time to Hemostasis (TTH), and secondary efficacy endpoints, Time to Ambulation (TTA), Time to Discharge Eligibility (TTDE), and Time to Discharge (TTD). The primary efficacy endpoint, TTH, was defined as elapsed time between device removal, i.e., device removal for Cardiva VASCADE VCS and sheath removal for manual compression, and first observed and confirmed arterial hemostasis (no or minimal subcutaneous oozing and the absence of expanding or developing hematoma). TTA was defined as the elapsed time between device removal, i.e., device removal for Cardiva VASCADE VCS and sheath removal for manual compression, and when ambulation was achieved (patient standing and walking at least 20 feet without re-bleeding). TTDE was defined as the elapsed time between device removal, i.e., device removal for Cardiva VASCADE VCS and sheath removal for manual compression, and when the patient was eligible for hospital discharge based upon an assessment of the access site.

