## EXTRA-VASCULAR COLLAGEN PATCH DEPLOYMENT AND DEVICE REMOVAL

12. Once the Disc location is verified, expose the extra-vascular resorbable Collagen Patch by unlocking the Black Sleeve. This is done by grasping the Lock with the left hand, between the thumb and the index finger, and grasping the Yellow-Blue Key with the right hand and then sliding the Yellow-Blue Key into the Lock until no blue color is visible, as shown in Figure 12. Once the Sleeve is unlocked and while still holding on to the Lock, remove the Clip with the right hand, and gently slide the Lock back along the angle of entry to retract the Black Sleeve as shown in Figure 13. The Black Sleeve will move freely after some initial resistance. A second resistance point may be felt after the sleeve is moved approximately 1.6 cm (0.6 inch).

Proceed to fully retract the Black Sleeve proximally to the Silver Handle. This action exposes the Collagen Patch extra-vascularly, which will swell at the arteriotomy site. The Collagen Patch may be allowed to swell for up to 30 seconds prior to removal of the VASCADE VCS Catheter. The Clip should be reapplied during the Collagen Patch swell period with minimal tension on the Catheter (Figure 14).

**NOTE:** If the Black Sleeve does not retract easily, recheck that the blue end of the Yellow-Blue Key is fully engaged in the Lock.

**NOTE:** If the Collagen Patch is removed during sleeve retraction, for non-anti-coagulated patients, collapse the Disc, remove the Catheter and apply manual compression, per institutional protocol. If the patient is anti-coagulated, the Clip may be applied to the VASCADE VCS Catheter on the skin surface to maintain temporary hemostasis. The device may then stay in dwelling in order to allow time for the ACT level to normalize. The device can then be removed followed by application of manual compression to achieve final hemostasis.

Fig. 12 – Unlock the Black Sleeve by sliding Yellow-Blue Key into the Lock

[figure not shown]

Fig. 13 – Retract the Black Sleeve by grasping the Lock and applying gentle upward tension toward the Silver Handle

Fig. 14 – Reapply Clip during the Collagen Patch swell period

Fig. 15 – Grasp Green Tube prior to collapsing the Disc

Fig. 16 – Collapse the Disc by pressing on the Black Actuator Tip

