13. After patch swell time ( $\leq 30$  seconds) has elapsed, remove the Clip. Rest the palm of the hand on the patient and grasp the green tube between the thumb and the index finger as shown in **Figure 15**. With slack in the catheter, collapse the Disc by pressing on the Black Actuator Tip as shown in **Figure 16**. When the Disc is fully collapsed, the Green Segment should not be visible for 6/7F device, or only a small portion, approximately 1mm, may be visible for the 5F device. While keeping the green tube stationary pull back the VASCADE VCS Catheter proximally. The Catheter Handle will move approximately 1.5cm while the green portion of the catheter remains stationary. This action slides the collapsed catheter Disc by the Collagen Patch while maintaining the position of the Collagen Patch. Once this initial movement has occurred, let go of the Green Tube. Gentle manual compression may be applied at the arteriotomy site. Remove the VASCADE VCS Catheter, and apply manual compression.

**Alternative Technique:** AFTER 15-30 seconds of patch swell time and PRIOR TO collapsing the Disk, remove the Clip. Rest the palm of the hand on the patient and grasp the green tube between the thumb and the index finger as shown in **Figure 15**. Push the green tube in the proximal direction approximately 1.5 cm while gently pulling back on the VASCADE VCS Catheter to maintain Disk position against artery wall. The green tube may be slid back and forth 2-3 times in order to assure release of the Collagen patch from device. Upon completion of this step, apply proximal compression, collapse the Disc by pressing on the Black Actuator Tip as shown in **Figure 16**. Gentle manual compression may be applied at the arteriotomy site. Remove the VASCADE VCS Catheter, and apply manual compression.

14. Observe for arterial hemostasis. Manual compression can be used to decrease or stop any tract ooze until full hemostasis is achieved.

---

[figure not shown]

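### The start time T5 of the primary outcome TTH is not tied to device removal, the event from which TTH is defined

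*Combined protocol and SAP*

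**What the plan says.** The synopsis and Section 8.1 agree on the start event. Section 8.1 reads: "Time to hemostasis (TTH) is defined as the elapsed time between Cardiva VASCADE™ VCS removal and first observed and confirmed arterial hemostasis". It sets TTH = T6 − T5, recorded to the second. Section 8.2 also runs time to ambulation (TTA) and time to discharge (TTD) from device removal, and uses T5 for both.

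Section 7.4.3, which lists what sites must write on the source worksheet, describes T5 as the "time that VASCADE VCS was deployed and/or removed and adjunctive compression started". T4 is insertion of the device and T6 is arterial hemostasis. No other item covers removal.

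Two further places bear on how T5 is read. The adjunctive compression guidelines say that "adjunctive compression at the site may be used until arterial hemostasis is achieved". Section 18.2 defines adjunctive compression as "Moderate manual compression at the arteriotomy site immediately after VASCADE VCS deployment, applied as an adjunctive measure to facilitate TTH".

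For the analysis, Section 9.2.2.1 states: "Ninety-five percent confidence intervals will be presented for means and medians".

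**The concern.** The T5 wording puts up to three events under one time stamp: deployment, removal and start of compression. When they occur at different moments, nothing in the protocol says which one governs. One site could record removal and another collagen release, and both would be following the text.

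The registry is descriptive, so the TTH estimate and its interval are its main product. Starting the clock at deployment lengthens TTH for a reason unrelated to how well the device seals. A larger sample would not remove that error, and it could show up as a difference between sites.

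Section 1.1 also says the data are to be collected consistently with the RESPECT design, and it criticizes published studies for inconsistent definitions. The IFU reports that in RESPECT "TTH, was defined as elapsed time between device removal, i.e., device removal for Cardiva VASCADE VCS and sheath removal for manual compression" was the starting point. A registry TTH timed partly from deployment would not be the same measure.

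**Working it through.** **1. Are deployment and removal separate events?** Yes. IFU step 12 exposes the collagen and then says: "The Collagen Patch may be allowed to swell for up to 30 seconds prior to removal of the VASCADE VCS Catheter". Removal comes in step 13. The alternative technique in step 13 gives a swell of 15 to 30 seconds.

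**2. Does the reference to compression fix T5 at removal?** Not securely.
- Compression is optional, so it cannot anchor every subject.
- Section 18.2 ties it to deployment, not removal.
- IFU step 13 allows some before the catheter is out: "Gentle manual compression may be applied at the arteriotomy site. Remove the VASCADE VCS Catheter, and apply manual compression".

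**3. Inputs for size.** The plan gives no precision figure to reproduce; Section 9.3 only judges 100 subjects sufficient. From the IFU:
- Table 4, RESPECT VASCADE interventional arm: TTH mean 5.5, SD 6.3, median 3.3 minutes; median TTA 4.1 hours; median TTD 23.4 hours.
- Table 7, all VASCADE subjects: 51, 136 and 195 of 275 had hemostasis by 2, 3 and 4 minutes. No interventional-only table is given.
- Gap *d*: 15 or 30 seconds of swell. Handling time is not stated and is left out.
- Share *p* of subjects timed from deployment: unknown; 25%, 50% and 100% are assumed.

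**4. Swell relative to median TTH.** 0.5/3.3 = 15.2%; 0.25/3.3 = 7.6%.

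**5. Mean.** Shift = *p* × *d*. With *d* = 30 s this is 7.5, 15 or 30 s, or 2.3%, 4.5% or 9.1% of 5.5 minutes. The 95% half-width at n=100 is 1.96 × 6.3/√100 = 1.23 min, about 74 s. The shifts are therefore about 10%, 20% and 40% of the half-width.

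**6. Median.** Linear interpolation of Table 7:
- Median: 3 + (137.5 − 136)/59 = 3.03 min.
- Ranks 40 and 61 of 100 (exact coverage 96.5%) give 2 + (110 − 51)/85 = 2.69 min and 3 + (167.75 − 136)/59 = 3.54 min.
- Half-width: (3.54 − 2.69)/2 = 0.42 min, about 25 s.

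The shifted median solves (1 − *p*)F(*x*) + *p*F(*x* − *d*) = 0.5. For *p* = 0.5 and *d* = 0.5 min, write *x* = 3 + *y*. In counts out of 275 this is 0.5(136 + 59*y*) + 0.5(51 + 85(0.5 + *y*)) = 137.5. So 114.75 + 72*y* = 137.5 and *y* = 0.316. The shift is 0.316 − 0.025 = 0.291 min = 17.4 s. All cases:

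| Share timed from deployment | Median shift, *d* = 15 s | Median shift, *d* = 30 s | Mean shift, *d* = 30 s |
|---|---|---|---|
| 25% | 4.7 s | 9.6 s | 7.5 s |
| 50% | 8.6 s | 17.4 s | 15 s |
| 100% | 15 s | 30 s | 30 s |

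**7. TTA and TTD.** 0.5/246 min = 0.20% of median TTA; 0.5/1404 min = 0.04% of median TTD. Both are negligible.

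**The case against.** The best defense is that T5 was always meant to be removal. Section 8.1 names removal and gives T6 − T5 in the same paragraph. Section 7.4.3 opens by using deployment for the whole IFU procedure, which ends with the catheter out. The footnote to T5 concerns taking the device out and converting to manual compression. The wording may therefore cover two cases, deployed then removed and removed without deployment, with removal as the time in both. This is plausible and probably the intent. It does not settle the matter, because the wording literally admits deployment alone and no section rules that out.

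Several points on size stand:
- The affected shares are assumptions, and 30 seconds is the IFU maximum.
- The early compression in step 13 of the standard technique comes after the swell, so a clock started there would be early only by brief handling time. The 15 to 30 seconds arise only if T5 is taken at collagen release.
- The median half-width uses all VASCADE subjects. About half (136 of 275) were diagnostic, with less spread (SD 4.2 against 6.3 minutes). It is probably too narrow for this interventional registry, so the median's sensitivity is somewhat overstated.
- The median shift exceeds its half-width only when every subject is affected, which is a uniform offset rather than a mixture.
- RESPECT excluded clinically significant peripheral vascular disease, so comparability is already limited.
- Timing from deployment lengthens TTH and does not flatter the device.

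The worksheet and eCRF are not in the documents. If they already record removal separately, only the protocol wording is at fault. Training and sponsor attendance at early cases may also reduce misreading, but they do not replace a definition.

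**Conclusion.** The concern holds. The protocol defines its primary performance outcome from removal and computes it from a time stamp that can mark another event.

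The likely effect is modest. It is at most 30 seconds of swell per subject in routine cases, plus unstated handling time. At assumed shares of 25% to 50% and a 30-second gap, the median moves by about 0.4 to 0.7 of its half-width (9.6/25 and 17.4/25) and the mean by 0.1 to 0.2. These figures assume RESPECT-like TTH and n=100. How often sites would depart from removal cannot be determined from the documents.

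The IFU also allows the device to stay in place for an unstated time in anti-coagulated patients when the collagen is not left at the site. The gap there could be longer, but it cannot be sized.

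The correction should be made because mixed start times may not be recoverable afterwards. The fault does not undermine the design, and TTA and TTD are practically unaffected.

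**What to change.** In Section 7.4.3, and on the worksheet and eCRF, define T5 as the time the VASCADE VCS was removed from the body, whether or not collagen was deployed. If collagen release (or its attempt) and start of compression are of interest, record each in its own field and keep both out of the outcome formulas. State that TTH = T6 − T5, TTA = T7 − T5 and TTD = T8 − T5 all run from removal. In Section 8.2, correct the formula closing the TTD paragraph, which is labelled TTA instead of TTD; this is a slip with no effect on the analysis.

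The cost is one reworded time stamp, one corrected label and at most one or two optional time fields. Device handling does not change.
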